### **9.3.3 Covariates**

These covariates will be used as patient characteristics for the overall population with the primary outcome events.

1. History of stroke or transient ischemic attack yes/no
2. History of myocardial infarction yes/no
3. History of heart failure yes/no
4. History of diabetes mellitus yes/no
5. History of dyslipidemia
6. History of arterial hypertension yes/no
7. History of peripheral artery disease
8. History of kidney impairment
9. History of valvular disease
10. History of liver disease
11. History of dementia
12. History of trauma
13. History of fracture
14. Nursing home resident
15. History of bleeding
16. Charlson co-morbidity index [3]
17. Concomitant medication yes/no for the following:
  - a. aspirin
  - b. clopidogrel
  - c. angiotensin receptor blockers (ARB) or angiotensin converting enzyme inhibitors (ACE)
  - d. beta-blocker
  - e. amiodarone
  - f. calcium-channel blocker (CCB)
  - g. diuretics
  - h. statins
  - i. proton-pump inhibitor
  - j. H2 receptor antagonist

The disease, Charlson co-morbidity index and concomitant medication are defined as [Table 1-Table 4](#). Nursing home resident is defined as MDV codes 113011710, 113016010, 114020910.

Table 1

Definition of clinical history

Disease	Definition	
	ICD10code	prescription
Stroke or transient ischemic attack	I60-I64, G45	-
Myocardial infarction	I21-I23	-
Heart failure	I110, I130, I132, I420, I50	Prescribed furosemide (defined by generic name)
Diabetes mellitus	E100, E101, E109, E110, E111, E119, E14	Prescribed drugs used in diabetes (defined by Anatomical Therapeutic Chemical (ATC) code as A10)
Dyslipidemia	E78	-
Arterial hypertension	I10-I15	Prescribed 2 or more types of anti-hypertensive (defined in Table 2 )
Peripheral artery disease	I702-I709, I71, I739	-
Kidney impairment	N28	-
Valvular disease	I059, I089, I358, I38, I48	-
Liver disease	K70-K77	-
Dementia	F00-F03, G30	-
Trauma	S00-S09, I620, M125, M164, M165, M172, M173, M191, M483, M872, S065, S066, S081, S089, S130, S18, S230, S480, S481, S532, S533, S580, S581, S589, S633, S634, S680, S681, S684, S688, S689, S780, S789, S889, S980, S981, S982, T050, T053, T058, T059, T116, T136, T147, T794, T795, T796, T797, S271, S272, S330, S334, S382, S480, S481, S532, S580, S581, S589, S633, S634, S680, S681	-
Fracture	M484, M80, S02, S12, S22, S32, S42, S52, S62, S72, S82, S92, T02, T08, T10, T12, T142	-

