Bleeding (gastro-intestinal, etc.)	K25-K29, K922, R04, R31, R58, K250, K260, K270, K280, K290, S063, S064, S065, S066	-

Table 2

Definition of anti-hypertensive

Class/type	ATC code
CCB	C08A0
ARB	C09C0
ACE	C09A0
Diuretics	C03A1, C03A2, C03A3, C03A7, C03A9
Thiazide diuretic	C03A3 (Thiazide, plane), C02D0 (Rauvolfia alkaloids)
Beta blocker	C07A0
Alpha-adrenoreceptor antagonists	C02A2
Potassium-sparing agents	C03A1
Others	C02A1 (Antihypertensives), C02A3 (Antihypertensives for pulmonary arterial hypertension), C09X0 (Other agents acting on the renin-angiotensin system)
Combination agents	C09D1 (ARB and diuretics), C09D3 (ARB and CCB)

Table 3

Definition of disease/conditions and weighted index for Charlson co-morbidity score

Score	Desease/conditions	Definition (ICD-10 code)
1	Myocardial infarct	See Table 1
1	Congestive heart failure	I110, I130, I132, I500
1	Peripheral vascular disease	I70-I74, I77
1	Cerebrovascular disease	I60-69
1	Dementia	See Table 1
1	Chronic pulmonary disease	J40-J47, J60-J67, J684, J701, J703, J841, J920, J961, J982, J983
1	Connective tissue disease	M05, M06, M08, M09, M30-M36, D86
1	Ulcer disease	K221, K25-K28
1	Mild liver disease	B18, K700-K703, K709, K71, K73, K74, K760
1	Diabetes mellitus	See Table 1
2	Hemiplegia	G81, G82
2	Moderate/severe renal disease	I12, I13, N00-N05, N07, N11, N14, N17-N19, Q61
2	Diabetes mellitus with chronic complications	E102-E018, E112-E118
2	Any tumor	C00-C75
2	Leukemia	C90-C96
2	Lymphoma	C81-C85, C88, C90, C96

Table 3 (cont'd)

Score	Desease/conditions	Definition (ICD-10 code)
3	Moderate/severe liver disease	B150, B160, B162, B190, K704, K72, K766, I85
6	Metastatic solid tumor	C76-C80
6	AIDS	B21-B24

Table 4 Definition of concomitant medication

Drug	Definition	
	ATC code	Generic name
Aspirin	-	Aspirin, aspirin dihydroxyaluminum aminoacetate magnesium carbonate
Clopidogrel	-	Clopidogrel sulfate
ARB or ACE	C09A0, C09C0, C09D1	-
Beta blocker	C07A0	-
Amiodarone	-	Amiodarone hydrochloride
CCB	C08A0	-
Diuretics	C03A1, C03A2, C03A3, C03A7, C03A9	-
Statins	C10A1	-
Proton pump inhibitor	A02B2	-
H 2 receptor antagonist	A02B1	-

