## **9.7 DATA ANALYSIS**

### **9.7.1 Main analysis**

#### For the primary outcome

Incidence rate of emergency surgery and major bleeding due to fracture/trauma will be described with each number of patients with event, patient-year and 95% confidence interval overall and stratified by age (age <64, 65-74 and >75). Baseline characteristics of patients overall and stratified by age will be provided in a tabulated format.

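### The bleeding-history row in Table 1 takes K922 but not K920, K921, K625 or I850, so a patient whose only baseline bleeding record is one of those four codes is tabulated as never having bled

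*Combined protocol and SAP*

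**What the plan says.** Section 9.3.3 lists covariate "15. History of bleeding" and states "The disease, Charlson co-morbidity index and concomitant medication are defined as" in Tables 1 to 4. The matching row of Table 1, whose label begins "Bleeding (gastro-intestinal, etc", gives these ICD-10 codes: "K25-K29, K922, R04, R31, R58, K250, K260, K270, K280, K290, S063, S064, S065, S066". Its prescription column holds only a dash, so the diagnosis codes are the whole definition.

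On use, Section 9.3.3 says "These covariates will be used as patient characteristics for the overall population with the primary outcome events", and Section 9.7.1 says "Baseline characteristics of patients overall and stratified by age will be provided in a tabulated format".

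I85 appears in one other place: Table 3, under moderate/severe liver disease in the Charlson index, with the codes "B150, B160, B162, B190, K704, K72, K766, I85".

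**The concern.** The row counts an unspecified gastro-intestinal haemorrhage as a bleeding history but does not count melaena or haematemesis, the specific codes beside it in the same category. The protocol gives no reason, and none is apparent. Two patients with the same clinical event can therefore be classified differently, depending only on which code the hospital entered.

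At stake is the reading of one line in the baseline table. In a study of major bleeding under oral anticoagulants, readers will look at that line to judge the cohort. Sections 9.9 and 9.12 warn about unvalidated outcome codes, generalisability and visits to other institutions, but say nothing about how this covariate is defined.

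**Working it through.** No sample-size or precision formula applies, and the plan states no figure to reproduce. The check is whether each code falls inside the list.

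**Inputs.** The code list and the dash in the prescription column come from Table 1, and the Charlson entry from Table 3. The meanings of the four codes are the headings of ICD-10, the classification that the protocol uses for this table. The documents do not print them.

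**Step 1: expand the list.** K25-K29 becomes the blocks K25, K26, K27, K28 and K29. The other entries stand as written. A code counts as matched if it begins with a listed entry.

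**Step 2: test the codes.**

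| Code | ICD-10 meaning | Entry matched in the Bleeding row |
|---|---|---|
| K920 | haematemesis | none |
| K921 | melaena | none |
| K922 | gastro-intestinal haemorrhage, unspecified | K922 |
| K625 | anorectal haemorrhage | none |
| I850 | bleeding oesophageal varices | none |

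Exact matching in place of prefix matching would not help, because none of the four is printed in the row.

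**Step 3: look for a wider definition elsewhere.** K920, K921 and K625 occur nowhere in the protocol. I850 is reached only through I85 in Table 3, which feeds the Charlson index and not the bleeding covariate. A patient coded I850 alone would therefore score 3 Charlson points for liver disease and still be recorded as having no bleeding history.

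**Step 4: look inside the row.** K250, K260, K270, K280 and K290 are listed separately although K25-K29 already covers them. That redundancy suggests, but does not prove, a list merged from more than one source and not reconciled. It makes a deliberate exclusion of the four codes less likely.

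**Step 5: trace the covariate.** It does not appear in the criteria of Section 9.2, the outcome definitions of Section 9.3.2 or the analyses of Section 9.7.1, other than in the baseline table. No adjusted model is planned, and Section 9.5 plans no hypothesis test.

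**The case against.** The strongest reply is that nothing the study sets out to estimate depends on this row. That is correct: every incidence rate is the same with or without the four codes. Several stronger readings are tempting, and the documents do not support them.

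- **Every patient with such a bleed is missed.** A reader might infer this, but anyone who also has a K25-K29, K922, R04, R31, R58 or S063-S066 code is still counted. Only patients with no listed code are affected.
- **The prevalence of bleeding history is understated.** The omissions act in that direction, but the row also takes all of K25-K29, which includes ulcer and gastritis codes that do not specify haemorrhage. The two errors oppose each other, and the documents do not show which is larger.
- **Hundreds of patients are affected.** Assuming that 0.5% to 2% of the 62,888 patients in Section 9.5 have only an omitted code gives 62,888 × 0.005 = 314 to 62,888 × 0.02 = 1,258. No document supports those percentages. The 62,888 comes from a previous study, and Section 9.3.3 can be read as describing only patients with events, a smaller group.
- **The primary outcomes inherit the gap.** Section 9.3.2.1 refers to bleeding of any kind without a diagnosis list and does not point to Table 1. Reuse of this row for the outcomes is possible, but the plan does not state it.
- **Table 3 contradicts Table 1.** It does not. The Charlson table has a different purpose, and its use of I85 shows only that the category was at hand.

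It is also fair to say that adding four codes does not prove the list complete. That is a reason to review the whole row when it is edited, not a reason to leave the four codes out.

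**Conclusion.** The point holds as a minor defect. The rule as written gives false negatives for patients whose sole baseline bleeding record is K920, K921, K625 or I850, while the unspecified K922 counts as a bleed. The effect is confined to one descriptive characteristic.

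Its size cannot be computed from the documents, and the net direction of error in the tabulated prevalence is uncertain. The conclusion rests on two things: that Table 1 is the complete definition, as Section 9.3.3 says, and that the codes carry their standard ICD-10 meanings.

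**What to change.** In the Bleeding row of Table 1, replace K922 with K920-K922 and add K625 and I850 before programming starts. If the exclusion was intended, state the reason there instead. The cost is one edited row of a code table, with no new data and no change to design, outcomes or analysis.

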## 9.5 STUDY SIZE

This study plans no formal hypothesis testing.

The previous study 1160.279 has identified the patients with confirmed 6 months of baseline period and no OAC treatment (defining “treatment naïve” new starter population). The total of these patients was 62,888. The breakdown by OAC initiated was 7,441 for dabigatran, 23,412 for warfarin, 16,026 for apixaban, 12,779 for rivaroxaban and 3,230 for edoxaban. The average on-treatment follow-up period for pooled OAC in patients with at least one year of baseline period prior to index date excluding the time after switching from one OAC to another was approximately 0.3 year. The average on-treatment follow-up period for pooled

OAC including the time after switching with 6 months of baseline period is unknown, but should be longer than 0.3 year.

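### Table 2's anti-hypertensive types overlap, so counted by row a single C03A1 or C03A3 drug meets the two-type test in the hypertension definition

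*Combined protocol and SAP*

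**What the plan says.** In Section 9.3.3, the arterial hypertension row of Table 1 has two entries. The ICD-10 column gives I10-I15. The prescription column gives "Prescribed 2 or more types of anti-hypertensive" and refers to Table 2. The protocol does not say whether both columns must be met or either is enough.

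Table 2 heads its row labels as class or type and has ten rows. Four of them matter here:

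- Diuretics: "C03A1, C03A2, C03A3, C03A7, C03A9"
- Thiazide diuretic: "C03A3 (Thiazide, plane), C02D0 (Rauvolfia alkaloids"
- "Potassium-sparing agents": C03A1
- Combination agents: "C09D1 (ARB and diuretics), C09D3 (ARB and CCB"

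On the use of the variable, Section 9.3.3 says: "These covariates will be used as patient characteristics for the overall population with the primary outcome events". Section 9.7.1 plans baseline characteristics tabulated overall and by age. Section 9.5 states: "This study plans no formal hypothesis testing".

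**The concern.** A rule that requires two types works only if each drug belongs to one type. In Table 2, two codes belong to two types each, so one drug can pass a test that was presumably meant to require two. Whether a patient on a single drug passes then depends on which drug it is: a patient on one calcium-channel blocker or one ARB fails, and a patient on one C03A3 or C03A1 product passes. Nothing in the protocol gives a reason for the difference.

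What is at stake is the hypertension yes/no line of the baseline tables, overall and within age groups. Two programmers working from the same text could also produce different flags. The independent check of program code in Section 9.8 would not settle this, because the specification allows both results.

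**Working it through.** There is no stated figure to reproduce. The check maps each code in Table 2 to its rows.

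**1. Entries and distinct codes.** Entries by row: CCB 1, ARB 1, ACE 1, Diuretics 5, Thiazide diuretic 2, Beta blocker 1, Alpha-adrenoreceptor antagonists 1, Potassium-sparing agents 1, Others 3, Combination agents 2. The sum is 1 + 1 + 1 + 5 + 2 + 1 + 1 + 1 + 3 + 2 = 18 entries. There are 16 distinct codes, so 18 − 16 = 2 entries are repeats: C03A3 (Diuretics and Thiazide diuretic) and C03A1 (Diuretics and Potassium-sparing agents).

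**2. Score of a single drug, counting rows.**

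- C03A3 alone: 2 rows, passes.
- C03A1 alone: 2 rows, passes.
- Each of the other 16 − 2 = 14 codes alone: 1 row, fails. These include C02D0, and also C09D1 and C09D3, although each of the last two is labelled as two classes.

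Patients who also take a drug from a clearly different class, such as a beta blocker, have two types anyway. The overlap therefore changes the result only for patients with no such second class.

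**3. Score of a single drug, counting distinct codes or drugs.** C03A3 or C03A1 alone scores 1 and fails. The overlap disappears, but so does the table's grouping: C03A2 with C03A7, both in the one Diuretics row, would then count as two types.

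**4. Who changes status.** Let N be the cohort size.

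- Columns joined by OR: extra patients classed as hypertensive = N × P(only Table 2 drug is one C03A1 or C03A3 product, and no I10-I15 code).
- Columns joined by AND: extra patients = N × P(only Table 2 drug is one C03A1 or C03A3 product, and an I10-I15 code present).
- Patients missed through combinations follow the same two formulas, with one C09D1 or C09D3 product in place of C03A1 or C03A3.

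The documents give none of these probabilities and do not state the link, so neither the size nor the sign of the net error can be computed.

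**5. After repair.** With C03A1 kept only under Potassium-sparing agents and C03A3 only under Thiazide diuretic, there are 18 − 2 = 16 entries for 16 codes, one each. If the three diuretic rows are merged instead, 10 − 2 = 8 rows remain, and again every code has one row. Removing C02A3 leaves 15 codes. Counting C09D1 and C09D3 as their components then makes those two the only codes that score 2, by intention, and the other 13 score 1.

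**The case against.** The strongest reply is that the protocol never tells anyone to count table rows. In ordinary language two types means two different kinds of drug, and a sensible programmer would not count one product twice. This stands to the extent that the counting unit is unstated. It does not remove the point. Table 1 counts types, and Table 2 attaches that word to its rows. Five codes share the Diuretics row, so a type is not a code. Assigning each drug to its most specific row may be what was intended, but it is not written down.

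The second reply is that the diagnosis column limits the damage. That stands. Under AND, every extra patient already has an I10-I15 diagnosis, and the overlap only loosens the drug condition. Under OR, only patients without such a diagnosis change status.

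The third reply is that C02A3 does no harm alone, since it scores one type. That is also right. It matters only as the second type beside one other drug. It is worth removing because the table itself labels it for pulmonary arterial hypertension.

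A reader might infer three stronger things that the documents do not support:

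- **That hypertension is over-recorded.** The under-count of combinations works the other way, and no frequencies are given for either group.
- **That the error concentrates in heart-failure patients.** The protocol gives no prescribing pattern for C03A1 or C03A3. The only drug in its heart-failure definition is furosemide, by generic name.
- **That a number of misclassified patients can be obtained by applying some share to 62,888.** That count comes from the previous study 1160.279, no share is given, and passing the prescription test is not the same as being classed as hypertensive.

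**Conclusion.** The stated rule is faulty as Table 2 is laid out. Two of 16 codes let one drug meet a two-type test, and two combination codes with two classes each count as one. This rests on reading a type as a row of Table 2, which is how the table is headed; under a count of distinct codes or drugs, C03A1 or C03A3 alone would not pass.

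The consequence is small. Only the hypertension row of the descriptive baseline tables can move, by an amount and in a net direction that the documents do not determine. Eligibility, patient-years, incidence rates, their confidence intervals and the age strata do not use the flag. Hypertension is not a component of the Charlson index in Table 3, and no hypothesis test is planned. Severity is minor, but the repair is cheap and the rule should not be programmed as written.

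**What to change.** Revise Table 2 and the hypertension row of Table 1:

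1. Make the types mutually exclusive. Either keep C03A1 only under Potassium-sparing agents, C03A3 only under Thiazide diuretic, and C03A2, C03A7 and C03A9 under Diuretics; or merge the three rows into one type. The two options differ for a patient on both C03A1 and C03A3 (two types if split, one if merged), so the choice should be stated. If the rows are merged, say where C02D0 belongs.
2. Count C09D1 and C09D3 as their two component classes. Table 4 already treats C09D1 as ARB or ACE use, so this has a precedent in the plan. If the diuretic rows stay split, name the row to which the diuretic component of C09D1 is assigned.
3. Drop C02A3 from the count.
4. State that types are counted as distinct classes from the revised list, and whether the I10-I15 and prescription columns are joined by AND or OR.

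The cost is an edit to two tables and the matching code lookup. No new data are needed. The reported hypertension prevalence may change, in a direction that cannot be foreseen from the documents.

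### Table 2 lets one fixed-combination product count as a single anti-hypertensive type and counts a pulmonary-hypertension code toward arterial hypertension, so the baseline hypertension flag depends on packaging and on an unstated AND/OR link

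*Combined protocol and SAP*

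**What the plan says.** All of the material is in section 9.3.3 (Covariates).

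- **Table 1, arterial hypertension.** There are two columns: ICD-10 codes I10-I15, and a prescription entry, "Prescribed 2 or more types of anti-hypertensive", which points to Table 2. Nothing says whether a patient must satisfy both columns or either one.
- **Table 2.** Ten rows under the header Class/type. Combination agents form one row, holding "C09D1 (ARB and diuretics), C09D3 (ARB and CCB"). The row Others includes "C02A3 (Antihypertensives for pulmonary arterial hypertension"). The Diuretics row holds "C03A1, C03A2, C03A3, C03A7, C03A9". C03A3 appears again in the thiazide row ("C03A3 (Thiazide, plane), C02D0 (Rauvolfia alkaloids")), and C03A1 appears again as the only code under potassium-sparing agents. No instruction says how a type is to be counted.
- **Table 4.** The concomitant-medication entry for ARB or ACE lists C09A0, C09C0 and C09D1. It does not list C09D3.
- **Use of the variable.** Section 9.3.3 introduces the list with "These covariates will be used as patient characteristics for the overall population with the primary outcome events". Section 9.7.1 plans a table of baseline characteristics overall and by age. Section 9.5 adds: "This study plans no formal hypothesis testing".

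**The concern.** The criterion is meant to pick out patients treated with at least two kinds of blood-pressure drug. By Table 2's own labels, C09D1 and C09D3 each contain two kinds. A programmer following the table would nevertheless score such a product as one, so the flag would turn on whether two drugs come as one product or two.

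C02A3 raises a separate problem. The table's own label assigns it to pulmonary arterial hypertension, yet it counts toward a variable whose diagnosis codes are I10-I15.

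What is at stake is one descriptive figure: the share of patients with a history of arterial hypertension, overall and by age. Readers use that row to judge who was studied. As defined, it would partly reflect product packaging and another disease's treatment, and two programmers could produce different values from the same data.

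**Working it through.** The plan gives no prevalence to reproduce, so the check applies the definition literally to a set of drug patterns.

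**Inputs:** the ten Table 2 rows with their ATC codes, the threshold of at least 2 types, and the I10-I15 column of Table 1.

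**Step 1: count types.** By row = number of Table 2 rows containing at least one of the patient's codes. By code = number of distinct listed codes. By component = number of distinct drug classes, with combinations split, each code in one row, and C02A3 removed.

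| Drugs prescribed | By row | By code | By component |
|---|---|---|---|
| C09D3 only (fixed ARB + CCB) | 1, fails | 1, fails | 2, meets |
| C09D1 only (fixed ARB + diuretic) | 1, fails | 1, fails | 2, meets |
| C09D1 and C09D3 | 1, fails | 2, meets | 3, meets |
| C09C0 and C08A0 (separate ARB, CCB) | 2, meets | 2, meets | 2, meets |
| C09C0 and C03A9 (separate ARB, diuretic) | 2, meets | 2, meets | 2, meets |
| C09D3 and a beta blocker | 2, meets | 2, meets | 3, meets |
| C02A3 only | 1, fails | 1, fails | 0, fails |
| C02A3 and C02A1 | 1, fails | 2, meets | 1, fails |
| C02A3 and a beta blocker | 2, meets | 2, meets | 1, fails |
| C02A3 and a CCB | 2, meets | 2, meets | 1, fails |
| C03A3 only | 2, meets | 1, fails | 1, fails |
| C03A1 only | 2, meets | 1, fails | 1, fails |

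Three results follow.

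- A single combination product fails whether types are counted by row or by code. The two components given separately pass under both.
- C02A3 alone never meets the criterion. With a CCB or beta blocker it does, and without C02A3 the same patient would have 1 type.
- Counted by row, one C03A1 or C03A3 drug alone meets the criterion, because each code sits in two rows.

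**Step 2: carry the criterion into the final variable.**

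| Patient | OR, I10-I15 coded | OR, not coded | AND, I10-I15 coded | AND, not coded |
|---|---|---|---|---|
| One combination product only | yes | no (missed) | no (missed) | no |
| C02A3 + CCB or beta blocker | yes | yes (over-counted) | yes | no |

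Under OR, both errors are confined to patients without an I10-I15 code. Under AND, coded patients on one combination product are missed, and C02A3 helps only patients who already carry an arterial-hypertension code.

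**Step 3: size.** The number affected would be the cohort size times the share with the relevant drug pattern and code status. The documents give no prescription or hypertension frequencies, so this cannot be computed.

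**The case against.** The strongest reply is that Table 2 never says a combination counts as one type. That is right: one-type counting is read from the row layout. Table 4 even classes C09D1 by its ARB component, so the authors may have meant component counting throughout. This does not rescue the definition. Row counting and code counting both give 1 for a single combination product, component counting is stated nowhere, and Table 4 itself leaves out C09D3. The supportable statement is that the counting rule is missing and the literal readings give the wrong answer.

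Four stronger readings are tempting, and the documents do not support them.

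- *Hypertension is misclassified in both directions regardless.* The prescription criterion can err both ways, but what reaches the final variable depends on the AND/OR link and on each patient's I10-I15 code. Under AND, the over-counting route largely closes.
- *C02A3 plus any diuretic creates a false positive.* Counted by row, a C03A1 or C03A3 drug already meets the criterion alone, so C02A3 adds nothing there. The example works with C03A2, C03A7 or C03A9, or with a CCB or beta blocker.
- *A patient count can be had by applying a percentage to 62,888.* Section 9.5 reports that number as the new-starter count from a previous study, and no percentage can be anchored in the documents.
- *The study results are affected.* Hypertension as defined here is not a Charlson item in Table 3, enters no stated model, and is not part of any outcome definition.

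It is also fair to say that a two-drug threshold is only a proxy, and that where to set it is a matter of judgement. The point here is not the threshold. It is that the same treatment is scored differently by packaging, and that a code labelled for another disease is included.

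**Conclusion.** The point holds in limited form. Followed as written, by row or by code, Table 2 fails a patient on one C09D1 or C09D3 product and passes a patient on the same two classes as separate products. It also lets C02A3 supply one of the two types required for arterial hypertension. The first statement rests on counting by row or by code, since no rule is given. The second rests directly on the table's own label.

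The direction and reach of the errors are conditional on the unstated AND/OR link, and their size is unknown. The effect is limited to the hypertension row of the baseline table. No primary or secondary incidence rate, patient-year total or confidence interval changes. This is a minor definitional correction, worth making before the table is programmed.

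**What to change.** Four edits to section 9.3.3:

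1. State that types are counted by distinct drug-class component, so that C09D1 counts as ARB plus diuretic and C09D3 as ARB plus CCB.
2. Assign each ATC code to one row only. C03A1 and C03A3 now sit in two.
3. Remove C02A3 from the list used for arterial hypertension.
4. State in Table 1 whether the ICD-10 and prescription columns are joined by AND or OR.

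Edits 1 and 3 alone would not be enough. One C03A1 or C03A3 drug could still pass as two types under row counting, and the prevalence would still depend on an undefined link. The cost is a revised code table, one or two sentences of text, and the programming of one flag. No new data are needed.

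### The baseline kidney impairment row (Table 1, N28 only) shares no code with the protocol's own moderate/severe renal disease list (Table 3); the diabetes history row has a related, conditional gap

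*Combined protocol and SAP*

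**What the plan says.** Section 9.3.3 of the combined protocol and SAP lists the patient characteristics to be tabulated. They include "History of kidney impairment", a history of diabetes and the Charlson index. Section 9.7.1 plans baseline tables overall and by age.

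- **Kidney, Table 1:** "Kidney impairment N28". The prescription column is a dash.
- **Kidney, Table 3:** the two-point Charlson item for moderate or severe renal disease is "I12, I13, N00-N05, N07, N11, N14, N17-N19, Q61".
- **Diabetes, Table 1:** the codes are "E100, E101, E109, E110, E111, E119, E14", and the prescription column reads "Prescribed drugs used in diabetes (defined by Anatomical Therapeutic Chemical (ATC) code as A10". The protocol does not say whether the two columns combine as AND or as OR.
- **Diabetes, Table 3:** the one-point item refers back to Table 1. A separate two-point item for diabetes with chronic complications is "E102-E018, E112-E118".

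The Abstract excludes dialysis and kidney transplant recipients. Section 9.11 gives presumed high bleeding risk among the reasons for its exclusions. Other renal disease stays in the cohort.

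**The concern.** Moderate or severe renal disease should be a subset of kidney impairment. If the two code lists do not overlap, one baseline table can give a patient renal points in the Charlson index and a 'no' in the kidney row.

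The plan itself treats the most severe renal patients as a bleeding-risk group to be removed. A reader will therefore look to the kidney row to see how much renal disease remains in the population behind the incidence rates. The Charlson total cannot answer that, because it does not show which condition produced the points.

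The diabetes history row raises a similar question: does a patient whose diabetes is coded only with complications have any diagnosis code that qualifies?

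**Working it through.** There is no planned figure to reproduce and no formula to apply. The check expands the code lists and compares them as sets, with a three-character category taken to include its subcodes.

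**Kidney**

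| Source | Content | Categories |
|---|---|---|
| Table 1 | N28 | 1 |
| Table 3 | I12, I13 | 2 |
| Table 3 | N00 to N05 | 6 |
| Table 3 | N07, N11, N14 | 3 |
| Table 3 | N17 to N19 | 3 |
| Table 3 | Q61 | 1 |

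Table 3 total: 2 + 6 + 3 + 3 + 1 = 15 categories. N28 is in none of them, so the overlap is 0.

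| Patient's renal codes | Kidney impairment row | Charlson renal points |
|---|---|---|
| N18, no N28 | no | 2 |
| N28 only | yes | 0 |
| N18 and N28 | yes | 2 |

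The row has no prescription condition, so the result does not depend on the AND/OR rule.

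**Diabetes**

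The first range in Table 3 ends at a lower number than it starts. I read it as E102-E108, which is an assumption. The complicated codes are then 7 (E102 to E108) + 7 (E112 to E118) = 14. None of the 14 is in the Table 1 list. E14 is listed whole in Table 1, so any complicated E14 code does count there.

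For a patient whose only diabetes code is E112:

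| Rule for the two columns | A10 drug prescribed | History of diabetes row |
|---|---|---|
| AND | yes or no | no |
| OR | yes | yes |
| OR | no | no |

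This patient scores 2 Charlson points for complicated diabetes in every case.

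**Scoring**

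No rule says that the higher diabetes item replaces the lower one. On diagnosis codes, a patient with both E119 and E112 scores 1 + 2 = 3. If the complicated codes were simply added to Table 1, the cross-reference in Table 3 would carry them into the one-point item. A patient with E112 alone would then also score 1 + 2 = 3.

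**The case against.** The strongest defence has four parts.

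1. **The labels differ, and Table 3 often uses its own lists.** It refers to Table 1 for myocardial infarct, dementia and plain diabetes. It sets separate lists for cerebrovascular, peripheral vascular and liver disease. So a difference between the tables is not in itself an error. This stands for heart failure. Table 1 has "I110, I130, I132, I420, I50" and the Charlson item has "I110, I130, I132, I500". A reader might infer that patients with other I50 subcodes wrongly lose a Charlson point, but nothing in the documents shows that the wider list is the intended one for an item labelled congestive heart failure. The argument does not rescue the kidney row, where the list for the more severe condition falls wholly outside the list for the general one.

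2. **Renal patients are not lost altogether.** This also stands. They keep their Charlson points, and the index is itself a listed characteristic. The fault is in one row.

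3. **The diabetes rows do not contradict each other.** The plain item in Table 3 points to Table 1, and complicated diabetes is scored separately. A reader might infer that diabetes is certainly understated. That is not supported: under an OR rule, patients with an A10 prescription are counted. What stands is that the history row has no diagnosis code for patients whose only E10 or E11 codes are complicated, and that the combining rule is missing.

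4. **No estimate depends on these rows.** Section 9.3.3 uses the covariates as patient characteristics, Section 9.5 plans no hypothesis test, and the rates are stratified by age only. This limits the point to description.

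**Conclusion.** The kidney point holds on the protocol's own lists. As written, the kidney impairment row counts none of the 15 categories that Table 3 calls moderate or severe renal disease, and a patient enters it only through N28. The direction is clear: patients with Table 3 renal codes and no N28 are shown as unimpaired. The number is not known, since the documents give no code frequencies.

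The diabetes point is secondary and conditional. Patients with only complicated E10 or E11 codes are missed from the history row under AND. Under OR they are missed only if they have no A10 prescription. The count of 14 codes rests on reading the misprinted range as E102-E108.

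A reader might infer that the incidence rates are biased. The documents do not support that, because these codes enter neither the outcome definitions nor the follow-up time, and no adjustment is planned. The effect is on the baseline tables and on how readers judge the population's renal and diabetic burden. Heart failure is not established as an error.

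**What to change.** 1. **Kidney impairment, Table 1:** replace the definition with the Table 3 renal set, keeping N28 as an addition if it is wanted.
2. **Diabetes history, Table 1:** add the complicated E10 and E11 codes, and state whether the code and prescription columns combine as AND or OR. The same statement should cover the other Table 1 rows that have a prescription entry.
3. **Diabetes, Table 3:** write the current uncomplicated codes into the one-point item in place of the cross-reference, so that the added codes do not flow into it. Count only the higher-weighted diabetes item per patient. Correct the misprinted range.
4. **Heart failure:** confirm that the narrower Charlson list is intended. No change is needed if it is.

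The cost is a few edits to code lists and two short rules, best made before programming. No new data are needed, and the outcome definitions and incidence rates are untouched.
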